The incidence rate (with 95% CI) will be calculated as the total number of first reports of an AESI divided by the total risk time of the patients. Additionally, the Kaplan-Meier method will be applied to estimate the median time from inebilizumab initiation to AESI onset if the number of events allows.

Milestones

Anticipated start of data collection (date of the first data extraction): April 2024

Anticipated end of data collection (date of the last data extraction): April 2028

Date(s) of study progress reports: Progress updates provided with each PSUR

Registration in the EU PAS register: September 2023

Final report of study results (to be submitted as a standalone procedure): December 2028

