6 RESEARCH METHODS

6.1 Study Design

This will be a non-interventional multi-center cohort study of patients initiating inebilizumab conducted with secondary data sources in France, Germany, Italy, the Netherlands, and Spain. The study will be based on a cohort-event monitoring design to capture both drug utilization and selected safety outcomes in patients initiating inebilizumab. The proposed study design allows for an efficient initial descriptive evaluation of AESI.

The **study period** in individual countries will start on different dates, depending on the launching time of the drug (the earliest in the second quarter of 2022) (Table 1). The end of the study period will be also country-specific (the latest in December 2027) and will depend on the dates of data availability in individual data sources (different lag times and data release dates).

Table 1 Study periods, by country

	France	Germany	Italy	Netherlands	Spain
	SNDS/ NOMADMUS	GKV	RISM	PHARMO	SIDIAP
Launch date (quarter, year)	Q2, 2022	Q3, 2022	Q2 2023	Q3, 2023	Q2, 2023
Start of study period	May 2022	Aug 2022	May 2023	Aug 2023	May 2023
End of study period	Dec 2026	Dec 2026	Dec 2027	Dec 2026	Sep 2027
Study period duration (months)	57	54	56	41	53

Q2, 2nd quartile; Q3, 3rd quartile

The study population will be constituted by a cohort of adult female and male patients diagnosed with NMOSD with entry trigger by inebilizumab initiation.

[figure not shown]
The **index date** (Day 0) will be defined as the date of first treatment (date of administration/prescription/dispensation, depending on data available in selected data sources) (Figure 1). Patients initiating the treatment will be identified throughout the study period. After the index date, enrolled patients will be followed for 12 months or censored at end of study period or loss of follow-up (death, disenrollment/de-registering) whichever occurs first.

A **baseline period**, including any time from when data are available up to the index date, will be used to establish comorbidities and NMOSD-related clinical characteristics, whereas a short period of 6 months prior to or at index date will be used to determine previous immunosuppressive therapies.

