6.5 Study Size

This is a descriptive study that will identify and characterize the patients who are treated with inebilizumab. There is no *a priori* hypothesis testing and no prespecified requirement of sample sizes. The final study size will be determined by the length of study period and uptake of inebilizumab in the countries and population covered in the data sources. In order to comply with pharmacovigilance reporting commitments, multiple data extractions are planned for EU countries. Slow uptake may impact on the ability to meet the study objectives; in this instance the feasibility of study completion within the proposed time frame and need for further data extractions, should be open to re-evaluation.

For this observational study, the interpretation of results focuses on the precision of estimands (proportions). [Table 3](#) presents the sample sizes across a range of expected incidences (of patient characteristics or AESI) and levels of precision. The sample sizes are derived assuming a normal approximation for the 95% confidence intervals (CI). Thus, in this study a pooled cohort of 400 patients across data sources would enable a patient characteristic (or AESI) with an assumed incidence of 1% to be estimated with a precision of +/- 1%, and for a patient characteristic (or AESI) with an assumed incidence of 4% to be estimated with a precision of +/- 2%.

Table 3 Sample Sizes of Patients Required to Estimate the Expected (True) Cumulative Incidence of a Patient Characteristic or AESI With 95% Confidence Intervals of Different Precisions (0.2% to 5%)

Estimated Incidence (%)	Precision 0.20%	Precision 0.50%	Precision 1%	Precision 2%	Precision 3%
0.30	2 872	-	-	-	-
0.40	3 826	-	-	-	-
0.50	4 778	764	-	-	-
0.70	6 675	1 068	-	-	-
0.80	7 621	1 219	-	-	-
1.00	9 508	1 521	380	-	-
2.00	18 823	3 012	753	188	-
3.00	27 947	4 471	1 118	279	124
4.00	36 878	5 900	1 475	369	164
5.00	45 617	7 299	1 825	456	203

AESI, adverse events of special interest

Feasibility – Patient estimates

Data sources and study countries were selected following a high-level feasibility assessment. It addressed the appropriateness of data sources for completion of this study regarding the ability to identify the target population and the presence of some variables of interest (such as results for AQP4 testing).

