The incidence rate and time to onset of AESI will be estimated in the overall study population. The incidence rates will be estimated separately for each AESI category, except infusion related reactions, as the total number of first reports of an AESI divided by the time at risk of the patients. The patients' time at risk will be counted from the initiation of inebilizumab treatment until occurrence of AESI, end of the 12-month follow-up or censoring. Incidence rate will be expressed as the number of first reports of an AESI per 1,000 patient-months.

Kaplan-Meier estimates of the median time from index date to AESI onset will be provided separately for each AESI category, except infusion related reactions, if number of events allows. If there is no AESI during the follow-up, the patient will be censored at the end of follow-up. Descriptive statistics on the time-to-event will be provided in further detail in the SAP.

Table 5 Overview of estimates of incidence and time to event defined for objective 3.

AESI category	Estimate	Time at risk	Event	Population
Infusion related reactions	Cumulative incidence	Day of infusion if date of inebilizumab administration available or 3 days following prescription/dispensation	All recorded reactions	Overall population
Serious Infections / Opportunistic infections	Cumulative incidence	12 months	All recorded infections during the follow-up	Overall population
	Cumulative incidence	Short periods	First infection during follow-up	Patients with complete 12-month follow-up
	Incidence rate	From index date to AESI, end of follow-up or censored*	First infection	Overall population
	Time to event	From index date to AESI end of follow-up or censor*	First infection	Overall population
Hepatitis B reactivations	Cumulative incidence	12 months	All recorded reactivations during the follow-up	Overall population
	Cumulative incidence	Short periods	First reactivation	Patients with complete 12-month follow-up
	Incidence rate	From index date to AESI end of follow-up or censor*	First reactivation	Overall population
	Time to event	From index date to AESI, end of follow-up or censor*	First reactivation	Overall population

AESI category	Estimate	Time at risk	Event	Population
Malignancies	Cumulative incidence	12 months	All recorded malignancies during the follow-up	Overall population
	Cumulative incidence	Short periods	First malignancy	Patients with complete 12-month follow-up

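### The Kaplan-Meier median, the only time-to-onset summary named for AESI, will not be reached at the incidences used for planning; risks at fixed times should replace it

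*Protocol*

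**What the plan says.** Protocol section 6.7.2.3 lists time to onset as one of three AESI measures, beside cumulative incidence and incidence rate. It specifies it thus: "Kaplan-Meier estimates of the median time from index date to AESI onset will be provided separately for each AESI category", and the sentence continues "except infusion related reactions, if number of events allows". The abstract has the same plan: "the Kaplan-Meier method will be applied to estimate the median time from inebilizumab initiation to AESI onset if the number of events allows".

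Three further statements fix what this median refers to:

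- Population (6.7.2.3): "The incidence rate and time to onset of AESI will be estimated in the overall study population". The time-to-event rows of Table 5 agree.
- Patients without an event (6.7.2.3): "If there is no AESI during the follow-up, the patient will be censored at the end of follow-up".
- Length of follow-up (6.1): "enrolled patients will be followed for 12 months or censored at end of study period or loss of follow-up".

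For the size of the risks, section 6.5 gives Table 3, titled in part "Sample Sizes of Patients Required to Estimate the Expected (True) Cumulative Incidence of a Patient Characteristic or AESI". Its rows run from 0.3% to 5%, and the text works with a pooled cohort of 400. No incidence is given for any single AESI category.

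**The concern.** Because event-free patients stay in the risk set until they are censored, the median describes all initiators, not only those who have an event. It is the time by which half of all initiators would have had the AESI. If only a few percent have one within 12 months, the curve stays far above 50% and there is no median to report.

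The attached condition does not screen for this. It refers to how many events there are, whereas estimability depends on how far the curve falls. A category could be judged to have enough events and the table would still show the median as not reached. At stake is whether one of the three Objective 3 measures, as named, says anything about when events occur.

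**Working it through.** **Inputs.** Cohort N = 400 and incidences p of 0.3% to 5% (section 6.5, Table 3); follow-up of at most 12 months (section 6.1); all initiators, event-free patients censored (section 6.7.2.3). The protocol gives no loss-to-follow-up rate, so the censoring patterns in step 4 are assumptions.

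**1. The plan's own figures.** Table 3 follows n = z² p(1 − p)/d² with z = 1.96.

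- p = 1%, d = 1%: 3.8415 × 0.0099 / 0.0001 = 380.3 (table: 380).
- p = 4%, d = 2%: 3.8415 × 0.0384 / 0.0004 = 368.8 (table: 369).

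All 30 filled cells reproduce. At N = 400 the half-widths are 0.98 points at 1% and 1.92 points at 4%, so the stated precision holds.

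**2. When the median exists.** It requires S(t) ≤ 0.5 at some t ≤ 12 months. With full follow-up, S(12) = 1 − p and the expected number of first events is 400p. Under a constant hazard the extrapolated median is 12 × ln 2 / (−ln(1 − p)).

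| 12-month risk | First events in 400 | S(12) | Extrapolated median (months) |
|---|---|---|---|
| 0.3% | 1.2 | 0.997 | 2,768 |
| 1% | 4 | 0.99 | 828 |
| 4% | 16 | 0.96 | 204 |
| 5% | 20 | 0.95 | 162 |
| 50% | 200 | 0.50 | 12 |

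The needed risk of 50% is ten times the top row of Table 3. As a rate it is 1,000 × ln 2 / 12 = 57.8 first events per 1,000 patient-months.

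**3. Chance of getting there with full follow-up.** The binomial probability of at least 200 events in 400 is about 2 × 10⁻¹⁴⁶ at 5%, 3 × 10⁻⁵ at 40%, 2.5% at 45% and 52% at 50%.

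**4. With early censoring.** In 4,000 simulated cohorts of 400 per scenario (constant hazard), at 1%, 4% and 5%:

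- no censoring before 12 months: median never reached;
- half the patients censored uniformly over 0–12 months: never reached;
- all patients censored uniformly over 0–12 months: reached in 1 cohort of 4,000 (0.025%), when an event fell in a nearly empty risk set.

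At a 20% risk the shares were 0%, 0% and 0.25%.

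**5. Event count against curve height.** A 5% risk in 4,000 patients gives 200 events, and S(12) is still 0.95: many events, no median. In the other direction, suppose a constant hazard and all 400 patients censored uniformly over 0–12 months. Then 150 events imply S(12) of about 0.36 and a median near 8 months. The count alone settles neither case.

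**6. What the same data can give.** At a 5% risk with full follow-up, the 12-month risk has a half-width of 1.96 × √(0.05 × 0.95 / 400) = 2.1 points. That is a usable figure where the median is not.

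**The case against.** The strongest defence is that little is lost. The median is promised only conditionally, and a sensible analyst would read the condition as covering estimability and leave the median out. The Kaplan-Meier curve and its 12-month value remain estimable. Section 6.7.2.3 defers further time-to-event descriptives to the SAP. Section 6.1, section 6.7.2.3 and the short-period rows of Table 5 already provide for monthly or 3-month incidences. Table 3 is a grid for patient characteristics or AESI alike, not a forecast by category.

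Much of this stands. A reader might infer that the time-to-onset analysis will yield nothing, or that the timing of events will go unaddressed. The documents do not support that, given the curve, the short-period incidences and the deferred descriptives. Nor do they show as a protocol figure that every category will miss the median, although that is very likely: with full follow-up it fails even at risks near 40%.

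A reader might also object that death is handled as ordinary censoring. Sections 6.1 and 6.7.2.3 do count death as loss to follow-up, but the protocol gives no mortality figure with which to size the effect, and it has no part in the present argument.

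Two things are left. The condition as written concerns the number of events, which is not the criterion. And the short-period incidences, which section 6.7.2.3 makes optional, are restricted to patients with complete 12-month follow-up. They leave out initiators who die, leave the data source or start late, and section 6.9 itself expects uptake to be concentrated late in the study period.

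**Conclusion.** The point holds in a limited form. The one time-to-onset summary that the protocol names is badly chosen: at 12-month risks of 0.3% to 5% the event-free probability stays at 95% or above, and the median will not be reached. The qualification about event numbers does not cure this.

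The conclusion assumes that the Table 3 range is a fair guide to AESI risk, but it has a wide margin. It would change only for a category whose 12-month risk approached 50%, or through an occasional late event in a nearly empty risk set under heavy censoring.

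Severity is minor. The study is descriptive, cumulative incidence and incidence rates are reported in any case, and no incidence estimate is biased by an unreached median.

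**What to change.** In section 6.7.2.3, the time-to-event rows of Table 5 and the abstract:

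- Replace the median with the Kaplan-Meier cumulative incidence (1 − S) at fixed times, e.g. 3, 6 and 12 months, with 95% CI and the full curve, in the overall population.
- Report the median only if the curve reaches 50%, and replace the condition on the number of events with that one.
- Add the median and quartiles of observed onset time among patients with an event, labelled as conditional on an event within 12 months. Objective 2 (section 6.7.2.2) already summarises time to switching in this way, among switchers only.

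Treating death as a competing event is an optional refinement.

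The cost is one sentence in 6.7.2.3, four table rows and a line of the abstract. Data, follow-up and software stay the same. Unlike the short-period incidences, the fixed-time risks use every initiator.

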- France: French National Health Data System (*Système National des Données de Santé* [SNDS]) and Multiple Sclerosis Registry (*Observatoire Français de la Sclérose en Plaques* [OFSEP])
- Germany: German Government Health Insurance (*Gesetzliche Krankenversicherung* [GKV])
- Italy: Italian Multiple Sclerosis and Related Disorders Registry (*Registro Italiano Sclerosi Multipla e Patologie Correlate* [RISM])
- The Netherlands: PHARMO Database Network
- Spain: Information System for Research in Primary Care (*Sistema d'Informació per al Desenvolupament de la Investigació en Atenció Primària* [SIDIAP])

Study size: In this study there is no a priori hypothesis testing and no prespecified sample size requirement. The final study size will be determined by the length of the study period and uptake of inebilizumab in the countries and population covered in the data sources. It is estimated that a pooled cohort of 400 NMOSD patients across data sources would enable a patient characteristic or AESI with an assumed incidence of 1% to be estimated with a precision of +/- 1% for 95% confidence interval (CI).

Data analysis:

Analyses will be performed for the overall study population and in sub-groups of special interest: patients concomitantly receiving other immunosuppressive agents and patients aged >65 years at index date.

To characterize new inebilizumab users, all patients of the study cohort will be described. Treatment patterns will be analysed only in patients with 12 months of complete follow-up and will be described as the number and proportion of patients who continue and discontinue treatment, respectively, who switch therapy and are exposed to add-on therapies. The median time to switching and the median time to use of add-on drugs will be described.

Estimation of the incidence will be conducted separately for each AESI category and will include cumulative incidence, incidence rate, and time to AESI onset. The cumulative incidence (with 95% CI) will be calculated as the total number of reports of an AESI during follow-up divided by the total number of patients initiating inebilizumab. The cumulative incidence estimates may also be calculated for shorter periods of time e.g., in monthly intervals after index date.

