6.2.2 Exclusion Criteria

No exclusion criteria will be applied.

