6.7.2.3 Objective 3: Incidence of AESI

The AESI evaluated in this study include the following categories: serious infections, opportunistic infections, hepatitis B reactivations, infusion related reactions, and malignancies. Analysis of AESI will include estimation of the cumulative incidence (i.e., risk), incidence rate, and time to AESI onset ([Table 5](#)). All analysis for AESI events (i.e., cumulative incidence, incidence rate and time-to-onset) will be performed using an intention-to-treat approach i.e., patients will be considered exposed regardless of subsequent discontinuation.

The cumulative incidence (with 95% CI) will be calculated separately for each AESI category considering the overall study population. For all AESI categories, except infusion related reactions, the cumulative incidence (with 95% CI) will be calculated as the total number of incident reports of AESI during the follow-up divided by the total number of patients. An algorithm to identify incident reports of AESI will be developed and described in the SAP. For infusion related reactions, the cumulative incidence (with 95% CI) will be calculated as the total number of all reports of infusion related reactions on the day of infusion (if date of inebilizumab administration is available) or during the first 3 days following prescription/dispensation (if date of inebilizumab administration is not available), divided by the total number of patients in the overall study cohort. Additional details of this calculation will be provided in the SAP.

The cumulative incidence estimates for each AESI category, except infusion related reactions, may also be calculated for shorter periods e.g., in monthly intervals after index date. In this case, the cumulative incidence in the first month after index date would consider patients with AESI reports in the first month in the numerator and patients with complete 12-month follow-up in the denominator. The cumulative incidence in the second month would consider patients with reports recorded only in the second month in the numerator and patients with complete 12-month follow-up included in the denominator. Due to the limited sample size, the time intervals may need to be clustered into e.g., 3-month intervals with the numerator and denominator adjusted accordingly. If sample size permits, the difference (with 95% CI) in cumulative incidence between 2 time periods of observation may be calculated.

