- Data sources relying on drug prescription/dispensation - and not administration - may result in exposure misclassification and bias in the treatment patterns characterization and time-to-event analyses. Additionally, reasons for treatment discontinuation, switching or augmentation are not possible to capture not allowing the documentation of changes in treatment.
- Some variables, such as drug dose, laboratory results of biomarkers and exams such as MRI may not be available in all data sources which will limit comparability and the ability of a more detailed characterization of inebilizumab users in those countries.
- Other variables, such as treatment indication, if not available in the data sources, will be based on pre-defined algorithms.
- The evaluation of drug safety using secondary databases does not allow for a causal assessment between inebilizumab exposure and the experienced outcome. NMOSD has been shown to be highly associated with other diseases including cancer (40). Additionally, an increased risk of malignancies or serious infections in NMOSD may be induced by the exposure to other immunosuppressive therapies (41,42). Please note, most malignancies have long latency periods in the absence of immunosuppression (43), and although immunosuppressive therapies possibly shorten the period (44), current study follow-up time may be too short (up to 1 year is the maximum) to identify some malignancies. Therefore, safety outcomes should be considered as signals of a possible safety concern of inebilizumab exposure.
- This study will capture safety outcomes that were serious enough to come to medical attention, which may underestimate the frequency of mild events. Additionally, misclassification is a possibility as it relies on the diagnosis codes. Identified serious infections, serious infusion related reactions or malignancies

represent a subgroup of all serious adverse events but for which the validity is expected to be higher.

- For some data sources, reporting of small numbers (e.g., <5) requires compliance with the local policies regarding data anonymization and the risk of patients' identification in observational research. For example, if a real value is 2, it may need to be presented as ≤ 4 in the results table. This may be a potential limitation for analyses that require stratification, such as the number of malignancies in a specific age groups. Furthermore, minimum and maximum values cannot be reported.

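### The protocol contradicts itself on which malignancies count as events, and sets no cancer-free baseline for the malignancy risk, rate or time to onset

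*Protocol*

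**What the plan says.** The protocol describes the malignancy estimates in several places.

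- **Section 6.7.2.3, text.** For every AESI category except infusion related reactions, the cumulative incidence is the "total number of incident reports of AESI during the follow-up divided by the total number of patients". It adds: "An algorithm to identify incident reports of AESI will be developed and described in the SAP". The population is stated as follows: "The cumulative incidence (with 95% CI) will be calculated separately for each AESI category considering the overall study population".
- **Table 5, malignancy rows.** There are four. The 12-month cumulative incidence takes as its event "All recorded malignancies during the follow-up", in the overall population. The short-period cumulative incidence uses the first malignancy, in patients with complete 12-month follow-up. The incidence rate and the time to event use the first malignancy, in the overall population, counted from the index date.
- **Abstract.** The cumulative incidence is the "total number of reports of an AESI during follow-up divided by the total number of patients initiating inebilizumab", without the word incident.
- **Section 6.2.2.** "No exclusion criteria will be applied".
- **Sections 6.1 and 6.3.2, Table 6.** Malignancy is a baseline comorbidity, ascertained from all available history before index.
- **Table 12.** The malignancy outcome is any code in ICD-9 140-209 or ICD-10 C00-C96. The infection and hepatitis B categories are marked as requiring hospitalization; malignancies are not.
- **Section 6.9.** "NMOSD has been shown to be highly associated with other diseases including cancer".

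**The concern.** A 12-month incidence should describe cancers that arise after inebilizumab is started. A patient under care for an existing cancer will often be coded for it again during the following year. If every recorded code counts, that patient becomes a case. If the event is the first malignancy, and first means first since index, the same patient is again a case, and probably an early one. No row of Table 5, and nothing in the text on time at risk, takes such patients out.

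Section 6.9 makes this more than a formality. It links NMOSD to cancer, notes that most malignancies have long latency, and asks that safety outcomes be read as possible signals. Genuinely new cancers within 12 months should therefore be few, and a handful of re-coded old ones could make up much of the count.

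**Working it through.** **1. The passages side by side (12-month cumulative incidence of malignancy).**

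| Place | Numerator | Denominator |
|---|---|---|
| Abstract | all reports | all initiators |
| Section 6.7.2.3, text | incident reports, algorithm in SAP | overall population |
| Table 5 | all recorded malignancies | overall population |

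Two of the three numerators include re-coded prevalent cancers and one does not. All three denominators keep patients with prior cancer.

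**2. The plan's own precision figure.** Table 3 uses n = z² p(1 − p)/d² with z = 1.96. For p = 1% and d = 1% this gives 380.3, against 380 in the table. For p = 4% and d = 2% it gives 368.8, against 369. Table 3 reproduces. With the 400 patients of section 6.5 and p = 1%, the half-width is 1.96 × √(0.01 × 0.99/400) = 0.98 percentage points.

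**3. What the choice of numerator does.** Inputs:

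- N = 400 and true incidence i = 1% in patients free of cancer at baseline. Both figures are taken from section 6.5, where 1% is an assumed value and not a malignancy estimate.
- Baseline prevalence p = 2% to 5%, and share re-coded within 12 months r = 50% to 100%. These are assumptions; the protocol gives neither.
- Each patient is counted once.

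All recorded malignancies counted: apparent risk = i(1 − p) + p·r.
Incident only, overall denominator: i(1 − p).
Incident only, malignancy-free denominator: i.

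| p | r | Events in 400, all recorded | All recorded | Incident / overall | Incident / malignancy-free |
|---|---|---|---|---|---|
| 2% | 50% | 3.92 + 4 = 7.92 | 1.98% | 0.98% | 1.00% |
| 2% | 100% | 3.92 + 8 = 11.92 | 2.98% | 0.98% | 1.00% |
| 5% | 50% | 3.80 + 10 = 13.80 | 3.45% | 0.95% | 1.00% |
| 5% | 100% | 3.80 + 20 = 23.80 | 5.95% | 0.95% | 1.00% |

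The excess over 1% on the all-recorded reading runs from 0.98 to 4.95 percentage points, so it equals or exceeds the planned half-width of 0.98. On the incident reading the error is 0.02 to 0.05 points, in the other direction.

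**4. Rate and time to onset.** If first malignancy means first since index, the rate takes the same extra events over slightly shorter risk time, so it is inflated by at least about the same factor. The planned time-to-onset statistic is a Kaplan-Meier median. With at most about 6% of patients having an event, the curve stays near 94% and the median is not reached on either reading.

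**5. Code lists.** Table 12 takes the whole of ICD-9 140-209. Table 6 omits, for example, 172, 196-199 and 208, and lists only selected 173 and C44 subcodes. A patient can therefore carry a Table 12 code before index without being recorded under Table 6 as having a malignancy.

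**The case against.** The strongest reply is that section 6.7.2.3 already limits the numerator to incident reports and leaves the algorithm to the SAP, which is not among the documents reviewed. Separating a new cancer from a re-coded old one is what such an algorithm is for, and it might also govern the first reports used for the rate and time to event. This stands in part. A reader might infer that baseline cancers are definitely going to be counted, but the protocol does not settle that. It also does not settle the opposite, because Table 5 and the abstract say something else about the same estimate. The algorithm is described as identifying reports; nothing says it changes who is in the denominator or at risk.

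Other replies also have force:

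- The all-recorded wording applies to one of the four malignancy rows. The other three use the first malignancy, which the protocol does not define relative to baseline.
- The absence of exclusion criteria concerns cohort entry. It does not by itself define an outcome-specific risk set.
- The protocol does not propose Table 6 as a screen for outcomes. The code difference matters only once a baseline screen is specified.
- A reader might infer that median time to onset would be pulled toward zero. At these event rates no median would be reached; only descriptive times among cases could shift.

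**Conclusion.** The contradiction is real: Table 5 and the abstract give one event for the 12-month malignancy risk, and the text of section 6.7.2.3 gives another. Separately, no malignancy estimate is tied to a cancer-free baseline, so the denominators and risk time include patients with prior cancer whichever numerator is used.

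The consequence depends on which wording is followed. Under Table 5 as written, re-coded prevalent cancers count and the bias is upward. Under the incident wording, only a negligible understatement of the cumulative incidence remains. The 2-6% range is an illustration resting on assumed prevalence and re-coding, with each patient counted once. It should not be read as a forecast, because the protocol offers no figure from which the size could be derived.

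**What to change.** 1. Change the malignancy event in Table 5 and the numerator in the abstract to match the incident wording of section 6.7.2.3.
2. Define an incident malignancy as the first Table 12 malignancy code in a patient with no Table 12 malignancy code in the baseline period. Using Table 12 on both sides removes the mismatch with Table 6.
3. Use that malignancy-free group as the denominator and risk set for cumulative incidence, rate and time to onset.
4. Report patients with prior malignancy separately, including codes recorded during follow-up, since they remain at risk of a new primary.

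The cost is a text edit and a slightly smaller malignancy denominator. No new variable is needed, because baseline malignancy is already planned. The limit is completeness: comorbidities are optional in the Italian register (section 6.4.4), and the length of look-back differs between sources. The share of patients with ascertainable baseline status and the available look-back should therefore be reported by data source.
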